4.4.2 Exclusion criteria

- Alcohol abstinence of >6 weeks prior to randomization/baseline visit
- Duration of clinically apparent jaundice > 3 months before baseline visit
- Other causes of liver disease including:
 - Evidence of chronic viral hepatitis (Hepatitis B or C)
 - Biliary obstruction
 - Hepatocellular carcinoma
- Evidence of current malignancy (except non-melanotic skin cancer)
- Previous entry into the study, or use of either prednisolone or any systemic steroids (equivalent to a dose of systemic prednisolone >20mg) within 6 weeks of screening.
- AST >500 U/L or ALT >300 U/L (not compatible with alcoholic hepatitis)
- Patients with a serum creatinine >220 μ mol/L (2.5 mg / dL) or requiring renal support (see below)
- Patients dependent upon inotropic support (adrenaline or noradrenaline). Terlipressin is allowed
- Variceal haemorrhage on this admission
- Untreated sepsis (see below)
- Patients with known hypersensitivity or contraindications to Canakinumab
- Patients with cerebral haemorrhage, extensive retinal haemorrhage, acute myocardial infarction (within the last 6 weeks) or severe cardiac arrhythmias (not including atrial fibrillation)
- Pregnant or lactating women

- Patients treated with other IL-1 inhibitors and biologics or any other immunosuppressants within 3 months of study participation.
- Known infection with HIV at screening or randomization
- History or evidence of tuberculosis (TB) (active or latent) infection
- Active ongoing inflammatory diseases other than AAH that might confound the evaluation of the benefit of canakinumab therapy
- Underlying metabolic, hematologic, renal, pulmonary, neurologic, endocrine, cardiac, infectious or gastrointestinal conditions, including neutropenia (ANC <1.5) and leukopenia, which in the opinion of the investigator immune-compromises the subject and/or places the subject at unacceptable risk for participation in an immunomodulatory therapy.
- Significant medical problems or diseases, including but not limited to the following: uncontrolled hypertension ($\geq 160/95$ mmHg), congestive heart failure [New York Heart Association status of class III or IV], uncontrolled diabetes
- Vaccination with a live vaccine within 3 month before baseline

Sepsis:

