7.1 Screening

- Informed consent from patient/legal representative
- Demographic details
- Inclusion and Exclusion criteria
- HIV test
- **Hep B & Hep C screening*
- Genetic sequencing for gene variant PNPL3
- Pregnancy test[^] (serum)
- **Alcohol consumption*
- Urinary ethyl glucuronide
- **Liver ultrasound (USS)*
- Past medical history including general history using the Charlson Index, liver-specific history (history of jaundice in past 3 months) and smoking history
- Prior/Concomitant medication
- **Complete physical examination, including height, weight, WHO performance status*
- **Vital signs (Temperature, systolic and diastolic blood pressure (BP), pulse rate)*
- **Laboratory tests: haematology, clinical chemistry (including electrolytes, creatinine, eGFR, LFTs [must include AST and GGT]), CRP and prothrombin time*
- **Disease scores: mDF, MELD, GAHS*
- **Evidence of GI bleed or sepsis in previous 7 days*
- **Acute kidney injury*
- **Infection/ sepsis/ SIRS screening including*
 - *Chest X-ray (CXR)*
 - *Blood cultures*
 - *Hepatic encephalopathy*
 - *Ascitic tap (in case required)*
 - *MSU*
 - *Urine culture*
- EDTA sample for host & bacterial DNA (16S)

[^] Not required in post-menopausal females.

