7.5 Schedule of Assessments

Table 1 lists all of the assessments and indicates with an ‘x’ at which visits the assessments are performed. Patients should be seen for all visits on the designated day, or as close to it as possible – the visit window/tolerance for each visit is given below the table. At a minimum, patients will be contacted for safety evaluations during the 90 days following randomisation to the study. At this final visit the adverse event and concomitant medications should be reconciled on the CRF. Documentation of attempts to contact the patient should be recorded in the source documentation.

Table 1: Assessment schedule

| | Screening | Baseline 6, 9, 11 | Day 7 ⁴ | Day 14 ⁴ | Day 21 ⁴ | Day 28 ^{2, 11} | Day 42 ^{1, 4} | On Discharge ¹⁰ | Day 90 ³ | Unscheduled |
|--|----------------|----------------------|--------------------|---------------------|---------------------|-------------------------|------------------------|----------------------------|---------------------|-------------|
| Informed Consent | X | | | | | | | | | |
| Demographic data | X | | | | | | | | | |
| Inclusion/Exclusion criteria | X | X | | | | | | | | |
| HIV test [^] | X | | | | | | | | | |
| Pregnancy test ⁺ | X ⁵ | | | | | | | | X | |
| Hepatitis B & C serology[^] | X | | | | | | | | | |
| Genetic sequencing (PNPLA3) | X | | | | | | | | | |
| Urinary ethyl glucuronide | X | X | | | | X | X | | X | |
| Alcohol consumption | X | | | | | X | X | | X | |
| Duration since admission to hospital | | | X | | | | | | X | |
| Medical history | X | | | | | | | | | |
| Prior/Concomitant medications | X | X | X | X | X | X | X | X | X | |
| Vital signs | X | X | X | X | X | X | X | X | X | X |
| Physical exam | X | X | X | X | X | X | X | X | X | |
| Weight | X | | | | | X ¹ | | X | X | |
| Height | X | | | | | | | | | |
| Calorie and protein intake | | X | X | X | X | X | X | X | X | |
| Randomisation | | X | | | | | | | | |
| IMP / placebo administration | | X | | | | X | | | | |
| Prothrombin time | X | X | X | X | X | X | X | X | X | |
| Haematology [%] | X | X | X | X | X | X | X | X | X | X |
| Clinical chemistry [%] | X | X | X | X | X | X | X | X | X | X |
| Serum CK18-M30/M65 sample | | X | X | X | X | X | X | X | X | |
| DF, MELD, GAHS scores | X | X | X | X | X | X | X | X | X | |
| Lille score | | | X | | | | | | | |
| Overt GI Haemorrhage assessment [§] | X | X | X | X | X | X | X | X | X | |

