7.6 Assessments

7.6.1 Patient demographics/other baseline characteristics:

Patient demographic and baseline characteristic data to be collected on all patients include: age, gender, ethnicity, source of patient referral, relevant medical history/ current medical condition present before signing informed consent. Where possible diagnoses but not symptoms will be recorded.

Detailed information on the patient's vaccination status (to be recorded as part of prior medication), disease diagnosis and disease related prior medications, surgical and medical procedures that occurred before signing informed consent will also be collected.

Investigators will have the discretion to record abnormal test findings on the medical history CRF whenever in their judgment, the test abnormality occurred prior to the informed consent signature.

7.6.2 Physical exam:

A complete physical examination will include the examination of general appearance, skin, neck (including thyroid), eyes, ears, nose, throat, lungs, heart, abdomen, back, lymph nodes, extremities, vascular and neurological. If indicated based on medical history and/or symptoms, rectal, external genitalia, breast, and pelvic exams will be performed. Weight and height will be measured as per the visit schedule. Physical exam includes WHO performance status.

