7.6.13 Other assessments

1. HIV test: An HIV test will be performed at screening (HIV test conducted within 6 months of screening may be accepted). Patients with a known infection with HIV at screening or randomisation will be excluded from participating in the trial.
2. Pregnancy Test (in females of reproductive age): A pregnancy test will be performed as a serum test at screening and pregnant patients excluded from participation. A urinary pregnancy test will be performed at day 90. If a subject or his partner becomes pregnant whilst taking part in the trial they will be followed up according to Section 9.6.
3. Hepatitis B & C Serology: Serology will be undertaken at screening (Hep B/C result performed within 6 months of screening may be accepted) and evidence of chronic viral hepatitis (B or C) will exclude the patient from participation.
4. Genetic sequencing: Genetic sequencing will be carried out at screening.
5. Alcohol consumption: Details on alcohol consumption will be collected at screening, day 28, day 42 and day 90.
6. Calorie and protein intake: Details on calorie and protein intake will be collected at all visits apart from screening.
7. Liver ultrasound (USS): A liver ultrasound will take place at screening only and is part of Standard of Care for the patients.
8. Stool and saliva samples will be collected at baseline and days 14, 28 and 90.
9. Exploratory BM serum to be collected (2 x 500ul) at baseline and all subsequent visits.

8 Statistical Considerations

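### Latent TB is an exclusion, but no scheduled assessment can detect an undiagnosed case, so such a patient can be randomised and given canakinumab

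*Combined protocol and SAP*

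**What the plan says.** Section 4.4.2 lists as an exclusion "History or evidence of tuberculosis (TB) (active or latent) infection". Both the active and the latent form are named.

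For the two other chronic infections that 4.4.2 names, the protocol schedules a test:

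- **HIV.** The criterion is "Known infection with HIV at screening or randomization", and section 7.6.13 states "An HIV test will be performed at screening".
- **Hepatitis B and C.** Section 7.6.13 requires serology at screening and says that "evidence of chronic viral hepatitis (B or C) will exclude the patient from participation".

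For TB there is no corresponding assessment. Section 7.5 introduces the schedule with the statement that "Table 1 lists all of the assessments".

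The items that could bear on TB are the history and the chest X-ray. Section 7.1 asks for "Past medical history including general history using the Charlson Index, liver-specific history (history of jaundice in past 3 months) and smoking history", and section 7.6.1 collects "relevant medical history/ current medical condition present before signing informed consent". The chest X-ray is part of the infection screen, which sections 4.4.2 and 7.6.7 define as chest radiography, urinalysis with culture if positive, an ascitic tap where there is ascites, and blood cultures if the patient is febrile.

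**The concern.** Latent TB gives no clinical sign for history or examination to pick up. If nothing in the schedule looks for it, an exclusion that names it can catch only patients whose infection is already on record.

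What is at stake is patient safety. Section 2.5 accepts that canakinumab may raise the risk of infection and gives this as a reason for restricting the population to lower-risk patients. A participant with undiagnosed latent TB could be dosed with no departure from the protocol. Monitors are asked in section 13.6 to confirm every participant's eligibility, but the protocol defines no result against which latent TB status could be verified.

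**Working it through.** The plan gives no figure on this point, so the check is a reading of every place where a TB test could appear, followed by counts.

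**1. Search of the assessments**

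| Place | TB test? | What could bear on TB |
|---|---|---|
| 7.1 Screening | None | Medical history, chest X-ray |
| 7.2 Baseline | None | Chest X-ray, repeat eligibility check |
| 7.3 and 7.4 Later visits | None | Chest X-ray |
| Table 1 and footnotes | None | Medical history, infection screen |
| 7.6.6 Laboratory tests | None | Nothing specific |
| 7.6.7 Infection screening | None | Chest radiography |
| 7.6.13 Other assessments | None | Nothing; HIV and hepatitis tests are listed here |

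**2. Counts**

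- Table 1 has 38 rows: 24 are marked in the screening column and 14 are not (24 + 14 = 38). Rows among the 24 that test for TB: 0. Rows are composites (the chest X-ray sits inside the infection screen), so this count shows only that no test is scheduled. It does not measure risk.
- Exclusions in 4.4.2 naming a specific chronic infection: 3 (viral hepatitis, HIV, TB). With a mandated screening test: 2 of 3.

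**3. What the existing checks can find**

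- History finds TB that is already known. It is weaker than usual here, because section 4.3 admits patients with encephalopathy who cannot consent, and their own exposure history may be unobtainable.
- The chest X-ray finds visible disease.
- The investigator-judgement exclusions act on what the investigator knows.

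None of these reveals undiagnosed latent infection with a normal film.

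**4. Exposure if allocated to canakinumab**

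- Day 1: 3 mg/kg.
- Day 28: a further 3 mg/kg if AST exceeds 2 x ULN, unless there was infection in the prior 28 days, MELD is above 27, or the PI is concerned about deterioration (section 3.6).
- Maximum: 2 x 3 = 6 mg/kg.

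The infection restriction would not be triggered by a silent latent infection.

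**5. How many patients**

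The documents give no prevalence p, so this cannot be estimated. For illustration only, the chance of at least one undiagnosed case among the 26 patients planned for the canakinumab arm is 1 - (1 - p)^26:

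| Assumed p | Expected cases among 26 (26p) | Chance of at least one |
|---|---|---|
| 0.5% | 0.13 | 12% |
| 1% | 0.26 | 23% |
| 2% | 0.52 | 41% |
| 5% | 1.3 | 74% |

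These are carriers, not harmed patients, and the values of p are assumptions. More than 26 may be dosed, since patients with negative histology are treated and then replaced (section 1.7).

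**The case against.** **The criterion's wording does not prove that testing was intended.** A reader might infer that excluding evidence of TB commits the protocol to look for it, as it does for hepatitis. The documents do not support that. The exclusion for current malignancy is also framed as evidence, yet no cancer screen is scheduled beyond the liver ultrasound. HIV is tested although its criterion speaks only of known infection. Wording therefore does not predict whether a test is scheduled. Other exclusions also lack a dedicated test, so a missing row is not in itself an error.

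**Sites may already test.** A reader might infer that no site tests for TB. The laboratory manual, eCRF manual and local instructions are not supplied and may call for it. Initiation visits train sites on eligibility (section 13.6), and 4.4.2 also excludes patients with contraindications to canakinumab. What the product information requires is not available here, so nothing is claimed about it.

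**A second dose is not automatic.** The section 3.6 restrictions apply, and infection is screened for at every visit (section 6.2). These limit the consequences of a missed case, but they do not detect latent infection.

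**Waiting for a result could do harm.** Footnotes 7 and 8 to Table 1 limit both the screening-to-baseline interval and the age of the baseline biopsy to 7 days. A late result or a repeat assay could force re-screening or a second biopsy. The sponsor chose not to wait 5 to 7 days for histology (section 1.7) and stresses rapid disease control (section 2.2). This objection stands, and the fix has to respect it.

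**Conclusion.** The gap is real. The protocol excludes latent TB by name but schedules nothing that could detect an undiagnosed case. The conclusion does not rest on how the criterion is phrased. It rests on three facts: the exclusion names the latent form, section 2.5 says canakinumab may increase infection risk, and both other named chronic infections have mandated screening tests.

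The size in patients is unknown. The documents support neither a prevalence nor a reactivation risk, and the illustrative range should not be used to argue severity. The finding is that the protocol does not require a test, not that untreated latent TB has been or will be missed at any site.

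This is a safety and eligibility matter. It leaves the sample size, alpha and primary analysis unchanged. It is worth correcting because the remedy is small.

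**What to change.** Add a latent TB blood test (for example an interferon-gamma release assay) to section 7.1, the screening column of Table 1 and section 7.6.13, with these rules:

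- Draw it with the first screening bloods. Accept a documented result from within 6 months of screening, as already allowed for virology.
- A positive result before randomisation excludes the patient.
- If the result is late or indeterminate, the PI decides on the first dose from TB history, exposure and chest X-ray, and records the reason. This protects the 7-day screening and biopsy windows.
- No second dose is given on Day 28 without a negative result. A positive result arriving after the first dose bars the second and is managed clinically. Section 3.6 should carry this restriction alongside the existing ones.

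Footnote 11 places Day 28 sampling before study drug, so a withheld second dose does not affect the primary biopsy comparison. It could affect Day 42 and Day 90 secondary measures in either arm.

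**Cost.** One assay per screened patient, with no extra visit or invasive procedure. A short amendment is needed, with matching changes to the information sheets, eCRF and laboratory manual and the usual approvals. Some patients will be extra screen failures or have a second dose withheld. A first-dose risk remains when the result is late or indeterminate. Assay turnaround is not in the documents.

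Rewording 4.4.2 to cover only known or radiologically visible TB would make the text consistent, but would leave the patient risk where it is.

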5.1 Account Creation

Each local user at the study sites must complete user training (appropriate to their role in the trial) for InForm after which an account will be created for them on the ISAIAH InForm database.

5.2 Source Data

Source documents include original documents related to the trial, to medical treatment and to the history of the participant, and adequate source documentation must be maintained to allow reliable verification and validation of the trial data. What constitutes the source data for this trial will be outlined in the study Monitoring Plan.

5.3 Patient Registration

After informed consent has been obtained each patient must be registered for the study via the ISAIAH InForm database. Registered patients will be allocated a unique Subject ID number. Each patient will retain this number for the duration of the study. The unique Subject ID number and patients' age will be the patient identifiers in the study data.

5.4 Patient Randomisation

After the patient is registered, the screening assessments will take place; please refer to the assessment schedule in section 7 for detailed description of screening assessments.

If eligible for the study, the patient will be electronically randomised via the ISAIAH InForm database to a study treatment group, but this will be blinded to the site staff (with the exception of designated unblinded study personnel) and the patient, by means of a unique code. If the patient is not eligible for the study, they are deemed a 'screening failure', and will receive treatment as per local standard care.

5.5 eCRF

Data will be collected through the electronic case report forms (eCRF) on the ISAIAH InForm database at each patient visit as scheduled below in Section 7. Details of procedures for eCRF completion will be provided in a study manual.

5.6 Procedure for breaking treatment code

In the event of a medical emergency where breaking the blind is required to provide medical care to the subject, the local principal investigators will have access to a mechanism that permits rapid unblinding should they feel this is necessary and are unable to contact the study team. Local SOPs describing the emergency unblinding procedure will be in place. The chief investigator recommends, but does not require, that the investigator contact him before breaking the blind. Treatment assignment should remain blinded unless that knowledge is necessary to determine subject

emergency medical care. The rationale for unblinding must be clearly explained in source documentation and on the electronic case report form (eCRF), along with the date on which the treatment assignment was obtained.

6. Concurrent Medication and Treatment

Many additional medications may be required. Concomitant medication may be given as medically indicated. Forbidden treatments are listed under section 6.4.

6.1 Alcohol withdrawal

Alcohol withdrawal therapy as required is allowed.

6.2 Infection / Sepsis

Patients who have infection or sepsis at screening or at any time during the study should be treated with antibiotics. Patients presenting with infection at screening visit will be eligible for randomization once the infection is under control. Antibiotics should be continued/given for the first two weeks after initiation in all patients. See Section 4.4 for further details.

Regular surveillance for infection or sepsis should be conducted throughout the study. Infection screening will be performed at every study visit.

6.3 Nutrition

All patients will receive supportive nutritional therapy. Patients will be offered nutritional supplements in the first instance. If they are unable to take these, they will be offered enteral nutrition via a nasogastric tube. An attempt should be made to provide 35-40 kcal/kg/day non-protein energy with 1.5g/kg/day protein. The responsible clinician will decide upon the use of other treatments such as terlipressin, for patients who are developing hepatorenal failure, acid suppression for prophylaxis against gastro-intestinal haemorrhage, antibiotics and vitamin supplementation.

6.4 Other treatments for Alcoholic Hepatitis

N-acetyl cysteine should not be used.

Patients must NOT be prescribed pentoxifylline or prednisolone during the treatment period of the study.

Other immunosuppressive treatments must not be used.

7. Investigations & Procedures

Please also refer to the tabulated Schedule of Assessments (Table 1) and the summary of treatment plan in appendix 1.

All patients must have freely given their informed consent before any trial-related procedures can be conducted.

Procedures marked '' written in italics are part of routine clinical practice and are listed only to denote that the data will be collected in the CRF

7.1 Screening

- Informed consent from patient/legal representative
- Demographic details
- Inclusion and Exclusion criteria
- HIV test
- **Hep B & Hep C screening*
- Genetic sequencing for gene variant PNPL3
- Pregnancy test[^] (serum)
- **Alcohol consumption*
- Urinary ethyl glucuronide
- **Liver ultrasound (USS)*
- Past medical history including general history using the Charlson Index, liver-specific history (history of jaundice in past 3 months) and smoking history
- Prior/Concomitant medication
- **Complete physical examination, including height, weight, WHO performance status*
- **Vital signs (Temperature, systolic and diastolic blood pressure (BP), pulse rate)*
- **Laboratory tests: haematology, clinical chemistry (including electrolytes, creatinine, eGFR, LFTs [must include AST and GGT]), CRP and prothrombin time*
- **Disease scores: mDF, MELD, GAHS*
- **Evidence of GI bleed or sepsis in previous 7 days*
- **Acute kidney injury*
- **Infection/ sepsis/ SIRS screening including*
 - *Chest X-ray (CXR)*
 - *Blood cultures*
 - *Hepatic encephalopathy*
 - *Ascitic tap (in case required)*
 - *MSU*
 - *Urine culture*
- EDTA sample for host & bacterial DNA (16S)

[^] Not required in post-menopausal females.

7.2 Baseline (pre-randomisation)

- Inclusion and Exclusion criteria
- Urinary ethyl glucuronide
- Concomitant medication
- **Dietary calorie and protein consumption*
- **Complete physical examination including WHO performance status*
- **Vital signs (Temperature, systolic and diastolic blood pressure (BP), pulse rate)*
- **Laboratory tests: haematology, clinical chemistry (including electrolytes, creatinine, eGFR, LFTs), CRP and prothrombin time*
- **Disease scores: mDF, MELD, GAHS*
- **Evidence of GI bleed or sepsis in previous 7 days*
- **Acute kidney injury*
- **Infection/ sepsis/ SIRS screening including*
 - *Chest X-ray (CXR)*
 - *Blood cultures (in case of fever)*
 - *Hepatic encephalopathy*
 - *Ascitic tap (in case required)*
 - *MSU*
 - *Urine culture (in case required)*
- EDTA sample for host & bacterial DNA (16S)
- Heparinised sample for PBMC (Monocyte oxidative burst + Monocyte phenotype)
- Serum CK18-M30/M65
- *Liver Biopsy at screening/pre-randomisation is Standard of Care*
- *HVPG measurement during trans-jugular biopsy procedure*
- Gene expression tissue sample
- Fibroscan
- PK/PD
- Exploratory/inflammatory BM serum
- Duration since admission to hospital
- Adverse events
- Stool and saliva sample

See Schedule of Assessments and Footnote Table for timeframe allowances and full notes relating to sample collection.

